	Gadoteric Acid Meglumine Salt: Patients who have undergone contrast-enhanced MRI using Gadoteric Acid Meglumine Salt contrast agent for clinical purposes.	Drug: Gadoteric Acid Meglumine Salt Injection (Jia Di Xian™)
Eligibility Criteria	
Inclusion Criteria:
 
 1. Patients aged 18 to 80 years old who require gadolinium-based CE-MRI; 2. Patients with renal function $30\text{ml/min}/1.73\text{m}^2 \leq \text{eGFR} < 90\text{ml/min}/1.73\text{m}^2$; 3. Patients who are able and willing to comply with the required inspection requirements. 
Exclusion Criteria:
 
 1. Patient who experienced allergic reactions to previous gadolinium based contrast agents; 	

	
 2. Patient who had used gadolinium based contrast agents within 3 months; 3. Patient with acute renal failure; 4. Patient who cannot comply with or cannot tolerate the necessary fluid replenishment procedures; 5. Patient with major mental illness, impaired consciousness or other diseases considered by researchers to affect observation.
Outcome Measure	
Primary Outcome indicators: Record the incidence of various adverse events;
 
Secondary outcome indicators:
 
 1. Changes of serum creatinine and inflammatory factors (TNF-α, hs-CRP, IL-6) before and after CE-MRI 2. Patient skin examination and evaluation: evaluation of relevant indicators of skin biopsy (proliferation of fibroblasts in subcutaneous tissue, thickening of collagen fiber bundles)
Enrollment	600 participants

I. Sponsor Information

(I) Name of sponsor

[name]

(II) Address of sponsor

Lishui Central Hospital, [name]

(III) Contact information of sponsor

[name]

(IV) Relevant qualification documents of sponsor

The relevant qualification documents of the sponsor will be provided in a separate letter.

II. Purpose and contents of clinical trial

(I) Purpose

To compare the incidence of adverse events of linear and macrocyclic gadolinium-based contrast agents for patients with mild to moderate renal insufficiency undergoing enhanced magnetic resonance imaging.

(II) Contents

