After intravenous injection of gadolinium contrast agent, it is mainly distributed in the extracellular fluid of the body, does not bind to serum albumin, does not pass through the healthy blood-brain barrier, is filtered by the glomerulus, and is excreted as a prototype; when the kidney function is normal, The plasma half-life is about 90 minutes, and the plasma clearance rate of patients with renal insufficiency will be slower.

(II) Safety data of clinical application so far

In 2016, Eric de Kerviler and others reviewed the 25-year clinical use of gadoterate meglumine (DOTAREM) and the safety data of phase I-IV clinical trials. In the safety data of phase I-IV Gadoterate meglumine clinical trials, 2822 patients, 241 (8.5%) patients, 405 adverse events occurred, 113 cases (4.0%) may be related to gadoterate meglumine. There were 27 serious adverse events (1.0%), including 2 cases (0.07%) related to gadoterate meglumine. No new adverse reactions were found in the post-marketing safety study, with adverse events <1.0%. During 25 years, 50 million injections, only 3797 patients had 8397 adverse reactions, the incidence of adverse reactions was extremely low (0.007%). Gadolinium diamine was approved for MRI diagnosis of adult central nervous system diseases in 1993. It is a non-ionic MR contrast agent. Like other paramagnetic contrast agents, it can shorten tissue relaxation time (T1 and T2, Mainly T1). The enhancement effect depends on the blood supply of the tissue. The contrast agent can be distributed in the blood vessel and extracellular space, and the enhancement effect is obvious. A Meta-analysis of 214,342 patients who used gadolinium-containing contrast agents included 42 documents. The incidence of all adverse reactions was 0.19% (397/214342), and the incidence of adverse reactions with gadolinium diamine was 2.52% (10/397).). Gadolinium diamine is the first reported NSF-related gadolinium-containing contrast agent, and its ligand is a non-ionic linear chelate. In risky subjects, 3%-18% of the contrast agent will have NSF.

V. Indications, contraindications and precautions of drugs

【Indications】

This product is only used for disease diagnosis.

MRI examination for the following diseases:

1. Brain and spinal cord disease
2. Spinal disease
3. Other systemic pathological examinations (including angiography)

【Contraindications】

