This experiment uses an electronic CRF form for manual review and computer inspection; follow the guidelines for filling in the CRF for this test; if there is questionable data after manual review or computer inspection, a data questioning form will be sent to the clinical trial unit and the investigator will sign and confirm the value Correction, data questioning and correction form should be kept.

(II) Statistical Analysis

1. Statistical Analysis Plan

The statistical analysis plan is led by the statistician, assisted by the data administrator, sponsor and researcher, and formulated through consultation. After the trial plan is finalized, statisticians are selected; when about 50% of the enrollment is completed, the statistical analysis plan is started, and the statistical analysis plan is determined when the enrollment of the last case is completed; the statistical analysis plan can be performed before the database is finally locked modify.

2. Sample size

This study is a post-marketing safety observation study, with a design sample size of 600 cases.

3. Statistical analysis sets and statistical methods

Because this trial is a safety monitoring study, the analysis set includes all patients who have used the study drug and have undergone safety evaluation.

The statistical analysis was done using SAS 9.4. This study does not estimate missing data.

All statistical tests are at the 5% level of significance, and the two-sided test may be expressed with a 95% confidence interval.

Describe the basic information of the patient, and use the mean, median, standard deviation, and range for continuous variables for statistical description. Categorical variables (nominal variables/ordinal variables) are described by frequency and frequency.

Calculate the number of adverse events, serious adverse events, adverse reactions and serious adverse reactions, the incidence and its 95% confidence interval, and the 95% confidence interval is calculated using the exact probability method. They are described separately according to the severity of adverse events and whether they are related to drugs.

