Taking adverse reactions and adverse events as dependent variables, taking gender, age, concomitant diseases, gadolinium diamine, gadoteric acid meglumine exposure, combined medication and other factors as independent variables, using Logistic regression to analyze the occurrence of adverse reactions or adverse events. Significant influencing factors, and estimate the odds ratio and its 95% confidence interval. The variables entered into the model will be confirmed in the statistical plan before the data is locked.

X. Trial summary and results publication

After the drug clinical trial summary is completed, at least there should be a statistical analysis report and a clinical trial summary report; after consultation with the investigator, the trial protocol or the results of the analysis after the analysis can be published, and the disclosure of confidential data is strictly prohibited.

The statistical analysis report is completed within one month after the database is locked, and the clinical trial summary report is completed within one month after the statistical analysis report is completed.

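### The only between-agent estimate is one logistic regression with no sparse-data method: probably adequate for all-cause adverse events, but thin to non-estimable for adverse reactions at the protocol's own rates

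*Combined protocol and SAP*

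**What the plan says.** Section II (I) gives the purpose as "To compare the incidence of adverse events of linear and macrocyclic gadolinium-based contrast agents" in patients with mild to moderate renal insufficiency. The Protocol Summary makes AE incidence the primary outcome and defines the groups by agent.

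Section IX (II) 3 then plans two things.

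- Counts, incidences and exact 95% confidence intervals for AEs, serious AEs, adverse reactions and serious adverse reactions. "They are described separately according to the severity of adverse events and whether they are related to drugs". Agent is not named as a breakdown, and no difference or ratio of incidences is named.
- A regression with AEs and adverse reactions as outcomes, listing "gadolinium diamine, gadoteric acid meglumine exposure, combined medication and other factors as independent variables, using Logistic regression" and reporting odds ratios with 95% confidence intervals. Both agents appear as exposures, no reference agent is given, and no exact or penalised method is mentioned.

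Under Section IX (II) 1, work on the full SAP starts at about half of enrolment, "the statistical analysis plan is determined when the enrollment of the last case is completed", and changes are allowed until database lock. Section IX (II) 3 explicitly leaves only the model variables to that later plan.

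Section IV (II) supplies the only background rates.

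- Gadoterate trials with 2822 patients: "241 (8.5%) patients, 405 adverse events occurred", and "113 cases (4.0%) may be related to gadoterate meglumine".
- Gadoterate after marketing: "No new adverse reactions were found in the post-marketing safety study, with adverse events <1.0" per cent.
- A meta-analysis of gadolinium agents: "The incidence of all adverse reactions was 0.19% (397/214342" patients).

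None of these is stated for renal insufficiency or for 24 months of follow-up.

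**The concern.** Maximum-likelihood logistic regression has no finite odds ratio for agent when one agent group has no events, and it is unstable when there are few events per model term. With 3/300 against 0/300 events, for example, the fit did not converge and returned a log odds ratio of 21.6 with a standard error of about 28,600. The same model is planned for a common outcome (all-cause AEs) and a potentially rare one (adverse reactions). If reactions are rare, the one between-agent estimate named for them may not exist, and a substitute would have to be chosen late.

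Coding is a second, smaller problem. If each patient receives exactly one agent, an indicator for each agent plus an intercept is collinear.

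**Working it through.** **Inputs.** N = 600 (Section IX (II) 2), given without event rate, effect size, power or split, so there is no sample-size calculation to reproduce. The quoted percentages do reproduce: 241/2822 = 8.5%, 113/2822 = 4.0%, 397/214342 = 0.19%. The 113 cases are taken as patients. Two figures in Section IV (II) are left out. The 2.52% for gadodiamide is 10/397, a share of all reactions and not an incidence. The 0.007% per injection would only be more extreme (600 × 0.007% = 0.04 events).

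**Assumptions.** Splits of 300:300, 400:200 and 450:150, with equal rates in both agents. Five model terms (sex, age, concomitant disease, agent, combined medication), or six if each agent is entered separately.

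**Step 1: events and empty groups.** Expected events = 600p. The chance that at least one group has no event is 1 − [1 − (1−p)^n1] × [1 − (1−p)^n2].

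At 0.19% and 300:300: 0.9981^300 = 0.565, so 1 − (1 − 0.565)² = 0.811. At 450:150: 0.9981^450 = 0.425 and 0.9981^150 = 0.752, so 1 − 0.575 × 0.248 = 0.857.

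| Rate and source | Events in 600 | Per term (5; 6 terms) | Empty group: 300:300; 400:200; 450:150 |
|---|---|---|---|
| 8.5%, AEs, trials | 51 | 10.2; 8.5 | all below 0.00001 |
| 4.0%, possibly related, trials | 24 | 4.8; 4.0 | 0.00001; 0.0003; 0.0022 |
| 1.0%, upper end of post-marketing AE figure | 6 | 1.2; 1.0 | 0.096; 0.150; 0.230 |
| 0.19%, reactions, meta-analysis | 1.1 | 0.2; 0.2 | 0.811; 0.831; 0.857 |

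**Step 2: adjusted model.** Simulation of 3,000 trials per setting: agent, three 50% binary covariates (sex, concomitant disease, combined medication) and a standard normal age, with no true effects, fitted by ordinary maximum likelihood.

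- Some coefficient not finite: 0% at 8.5%, at most 0.4% at 4.0%, 23–33% at 1.0%, about 95% at 0.19%.
- Agent coefficient not finite: 9–22% at 1.0%, 81–85% at 0.19%.

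**Step 3: what Firth gives.** In a 2×2 table the Firth odds ratio equals the odds ratio after adding 0.5 to each cell. For 6 v 0 this is (6.5 × 300.5)/(294.5 × 0.5) = 13.3. These tables are unadjusted, 300 per agent; risk differences carry Miettinen-Nurminen intervals.

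| Events | Ordinary OR (95% CI) | Firth OR (95% CI) | Risk difference, points |
|---|---|---|---|
| 26 v 25 | 1.04 (0.59 to 1.85) | 1.04 (0.59 to 1.85) | 0.33 (−4.23 to 4.91) |
| 12 v 12 | 1.00 (0.44 to 2.26) | 1.00 (0.44 to 2.25) | 0 (−3.34 to 3.34) |
| 5 v 1 | 5.07 (0.59 to 43.6) | 3.72 (0.74 to 36.4) | 1.33 (−0.36 to 3.55) |
| 6 v 0 | infinite | 13.3 (1.56 to 1733) | 2.00 (0.72 to 4.30) |
| 1 v 0 | infinite | 3.01 (0.16 to 440) | 0.33 (−0.94 to 1.87) |

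In simulation (400 trials per setting), Firth intervals covered a null agent effect in 94–98% of trials at 8.5%, 4.0% and 1.0%, and in at least 99% at 0.19%. In adjusted simulations that included a true odds ratio of 2, Firth matched the ordinary model at 8.5%, was slightly less biased and less variable at 4.0%, and stayed finite at 1.0%.

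**Step 4: coding.** An intercept plus two complementary agent indicators makes three columns of rank 2, so one agent term must be dropped.

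**The case against.** - **The primary outcome is not the rare one.** AEs under Section VI (IV) 1 need not be caused by the drug, and follow-up calls run to 24 months. The 0.19% is a rate of adverse reactions. This stands. A reader might infer that the trial could not state its main comparison; the documents do not support that. At 8.5% the model does not fail, and even at 1.0% the agent odds ratio is finite in 78–91% of simulated trials.
- **By-agent incidence is plainly intended.** The Protocol Summary, Section II (I) and Section III all point that way. This stands too. A reader might infer that incidences would be reported only pooled; the text simply does not say. That part is a clarification.
- **The SAP is still to come, and a sparse-event method is normal SAP content.** This limits the point to what the present protocol leaves open. It does not remove it, because only the model variables are explicitly deferred and the SAP is settled after most events on early visits will be known. Nothing suggests that results would steer the choice.
- **The text says only logistic regression, not ordinary logistic regression.** True, but with no exact or penalised method named, ordinary maximum likelihood is the natural reading.
- **Firth does little for the reader when events are rare.** An interval from 1.56 to 1733 is barely informative. This stands: the limit is the number of events.

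A reader might also infer that allocation is not randomised. Section VI (I) announces a trial process that is absent from the available text, probably a figure lost in conversion, so this cannot be settled.

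**Conclusion.** The point holds, mainly for adverse reactions. The single model is probably adequate for all-cause AEs (about 51 events at 8.5%) unless the post-marketing figure below 1.0% applies. For adverse reactions it ranges from thin at 4.0% (24 events) to usually having no finite agent odds ratio at 0.19% (about 1 event; an empty group in 81–86% of trials). The 4.0% comes from clinical trials and may be nearer to this setting, but the documents do not settle which rate applies.

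The result rests on the assumed splits, equal rates in the two agents, and rates not stated for this population or follow-up. The omission itself is certain; its consequence depends on the event rate. Severity: minor to should-fix, with medium confidence.

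**What to change.** In Section IX (II) 3, and carried into the SAP:

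1. Code agent as one indicator with a named reference, always kept in the model.
2. Fit the adverse-reaction model by Firth-penalised logistic regression with profile-penalised 95% confidence intervals and a few covariates named in advance. Do the same for AEs if events are few, with the threshold fixed beforehand (for example under 10 events per term), or use Firth throughout, which needs no threshold.
3. As a minor clarification, report the planned incidences and exact intervals by agent, and add the gadodiamide-minus-gadoterate risk difference with a 95% confidence interval. Miettinen-Nurminen is one suitable choice. Label the difference unadjusted, unless the trial-process content missing from Section VI (I) shows randomised allocation.

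The cost is protocol wording and slightly more analysis work. No new data or patients are needed, and the methods run in SAS 9.4, the named package. The downside is very wide intervals when events are rare. With about 6 events only very few covariates can be adjusted for, so possible residual confounding should be stated if allocation was not randomised.
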